6.2.4 Pulmonary function safety endpoints

- Treatment-emergent decrease of FEV₁ or FVC $> 20\%$ from baseline values
- Treatment-emergent decrease of percent of predicted FEV₁ or FVC > 20 percentage points from baseline values
- Change in FEV₁ and FVC from baseline, absolute and % of absolute change to all time points up to FU1

Confidential

- Among subjects with a decrease of > 200 mL and > 12% in FEV₁ or FVC from baseline to EOT1, reversibility is defined as a decrease of < 200 mL or < 12% in FEV₁ or FVC, respectively, from baseline to last available follow-up
- Change from baseline to FU1 vs change from baseline to EOT1 in FEV₁ or FVC (absolute and % of predicted)
- Change in lung diffusion capacity as assessed by the DL_{CO}, expressed in absolute change and % of predicted value from baseline to all time points up to FU1
- Change from baseline to FU1 vs change from baseline to EOT in DL_{CO} (absolute and % of predicted)
- (Serious) pulmonary AEs of special interest
- Withdrawal due to pulmonary reasons/AE

6.2.5 Other safety endpoints

- Treatment-emergent notable BP abnormalities [definition in Appendix 6]
- Treatment-emergent notable laboratory abnormalities [definition in Appendix 6]

6.3 Efficacy endpoints (exploratory)

The main efficacy endpoint is:

- Achievement of a partial or complete overall response at 24 weeks post-enrollment

Definitions for the efficacy endpoint are based on the draft 2014 NIH Consensus Development Project response criteria [NIH Therapeutic Response 2014]. Baseline or subsequent organ abnormalities that are not due to chronic GVHD are not evaluable for response (at the organ level).

6.3.1 Complete overall response definition

A complete overall response is defined as resolution of all reversible manifestations due to chronic GVHD in the following organs at the Week 24 assessment, resulting in:

- Skin: NIH Skin Score of 0 after previous involvement
- Mouth: NIH Modified Oral Mucositis Score of 0 after previous involvement
- Liver: normal ALT, alkaline phosphatase, and TBL after previous elevation of one or more
- Upper GI: NIH Upper GI Score of 0 after previous involvement
- Lower GI: NIH Lower GI Score of 0 after previous involvement
- Esophagus: NIH Esophagus Score of 0 after previous involvement
- Lungs: normal FEV₁ absolute value after previous involvement (normalization to FEV₁ \geq 80% predicted is considered a complete response)

- Eyes: NIH Eye Score of 0 after previous involvement
- Joint/fascia: Both NIH Joint and Fascia Score of 0 and photographic range of motion (P-ROM) score of 25 after previous involvement by at least one measure
- Global: Clinician Overall Severity Score of 0

6.3.2 Partial overall response definition

A partial overall response is defined as improvement in a measure for at least one organ without increase in measures for any other organ. A subject is considered as a partial responder at the Week 24 assessment, if there is a change of clinical benefit from baseline in at least one of the organs assessed (skin, mouth, liver, upper and lower GI, esophagus, lung, eye, and joint/fascia) and no progression in any other organ (stable NIH scores compared to baseline).

The proposed general guideline for defining partial response in a specific organ requires a change in score from baseline as follows:

- Skin: decrease in NIH Skin Score by at least 1 point
- Mouth: decrease in NIH Modified Oral Mucositis Score by at least 2 points
- Liver: decrease by 50% in ALT, alkaline phosphatase, or TBL
- Upper GI: decrease in NIH Upper GI Score by at least 1 point
- Lower GI: decrease in NIH Lower GI Score by at least 1 point
- Esophagus: decrease in NIH Esophagus Score by at least 1 point
- Lungs: increase by at least 10% predicted absolute value of FEV₁, as long as initial FEV₁ < 70% predicted
- Eyes: decrease in NIH Eye Score by at least 1 point
- Joint/fascia: decrease in NIH Joint and Fascia Score by 1 or more points or increase in P-ROM score by 1 or more points for any site
- Global: Clinician Overall Severity Score decreases by 2 or more points on a 0–10 scale

The proposed general guideline for defining progression in a specific organ requires a change in score from baseline as follows:

- Skin: increase in NIH Skin Score by at least 1 point, except from 0 to 1
- Mouth: increase in NIH Modified Oral Mucositis Score by at least 2 points
- Liver: increase by $\geq 2 \times$ ULN for ALT, alkaline phosphatase or TBL
- Upper GI: increase in NIH Upper GI Score by at least 1 point, except from 0 to 1
- Lower GI: increase in NIH Lower GI Score by at least 1 point, except from 0 to 1

- Esophagus: increase in NIH Esophagus Score by at least 1 point, except from 0 to 1
- Lungs: decrease by at least 10% absolute value of FEV₁, as long as final FEV₁ < 70% predicted
- Eyes: increase in NIH Eye Score by at least 1 point, except from 0 to 1
- Joint/fascia: increase in NIH Joint and Fascia Score by 1 or more points or decrease in P-ROM score by 1 or more points for any site
- Global: Clinician Overall Severity Score increases by 2 or more points on a 0–10 scale

6.3.3 Subject responder / non-responder definition

The endpoint is reached if the subject is considered a partial or complete responder at Week 24. The remaining subjects will be considered as non-responders, this includes subjects with stable disease and subjects with mixed response (defined as complete or partial response in at least one organ accompanied by progression in another organ).

In case of deviations from the planned schedule of prednisone treatment (with the exception of prednisone exceeding 1 mg/kg/day), the subject will still be eligible for the primary analysis.

6.3.4 Other efficacy endpoints

Other efficacy endpoints include:

- Need for rescue therapy for chronic GVHD
 - Rescue therapy is the addition of any new systemic or topical IS therapy, or exceeding baseline dose for any non-steroid IS, or exceeding glucocorticoid dose equivalent to prednisone > 1 mg/kg/day
- Partial or complete organ-specific response for the specific organ manifestation at Week 12 and Week 24 in subjects with a specific organ manifestation of chronic GVHD at study baseline
 - Affected organs limited to 2014 NIH consensus criteria organs of skin, eyes, mouth, esophagus, upper GI, lower GI, liver, lungs, and joints and fascia
- Partial or complete overall response at 12 weeks post-enrollment
- Complete response at Week 24
- Partial or complete overall response at latest evaluable assessment during the core study (Week 12 and Week 24)
- Average glucocorticoid daily dose over 24 weeks versus baseline dose
- Percent glucocorticoid dose at Week 24 versus baseline

Confidential

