	
The endpoint is reached if the subject is considered a partial or complete responder at Week 24. The remaining subjects will be considered as non-responders, this includes subjects with stable disease and subjects with mixed response (defined as complete or partial response in at least one organ accompanied by progression in another organ).
 
Other exploratory efficacy endpoints
 
• Need for rescue therapy for chronic GVHD
○ Rescue therapy is the addition of any new systemic or topical IS therapy or exceeding baseline dose for any systemic non-steroid IS or exceeding glucocorticoid dose equivalent to prednisone $> 1 \text{ mg/kg/day}$• Partial or complete organ-specific response for the specific organ manifestation at Week 12 and Week 24 in subjects with a specific organ manifestation of chronic GVHD at study baseline
○ Affected organs limited to 2014 NIH consensus criteria organs of skin, eyes, mouth, esophagus, upper GI, lower GI, liver, lungs, and joints and fascia• Partial or complete overall response at Week 12 post-enrollment• Complete response at Week 24• Partial or complete overall response at latest evaluable assessment during the core study (Week 12 and 24)• Average glucocorticoid daily dose over 24 weeks versus baseline dose• Percent glucocorticoid dose at Week 24 versus baseline 
Extension Treatment Period Endpoints
 
The same endpoints will be assessed in the Extension Treatment Period as were assessed in the Core Treatment Period, however adjusted for the corresponding visit schedule.

QUALITY OF LIFE ENDPOINTS	
Core Treatment Period Endpoints

Confidential

	
• Change from baseline to Week 12 and Week 24 in Lee Symptom Scale for chronic GVHD [Appendix 8]• Change from baseline to Week 12 and Week 24 in each of the subject-reported chronic GVHD symptoms (skin, eyes, mouth and genitals [Appendix 7 – Form B]).• Change from baseline to Week 12 and Week 24 in each of the patient-reported global ratings (Mild-Moderate-Severe Scale, Overall Severity Scale and 7-Point Change Scale [Appendix 7 – Form B]). 
Extension Treatment Period Endpoints
 
The same endpoints will be assessed in the Extension Treatment Period as were assessed in the Core Treatment Period, however adjusted for the corresponding visit schedule.

ASSESSMENTS	Refer to the schedule of assessments in Table 1.

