5.1.10 Specific dose-reduction, interruption, or premature discontinuation criteria

Ponesimod should be prematurely discontinued before initiating rescue IS therapy or other forbidden medications during the Core Treatment Period. Ponesimod should also be prematurely discontinued before initiating forbidden medications during the Extension Treatment Period. See Section 5.3.5.

Ponesimod-specific dose reduction, interruption, or premature discontinuation criteria are presented for a variety of conditions and scenarios grouped according to the following organ systems. These criteria apply during both the Core and Extension Treatment Periods:

- (1) Cardiovascular
- (2) Hematologic
- (3) Hepatobiliary
- (4) Immune/infection

- (5) Ocular
- (6) Reproductive/pregnancy
- (7) Respiratory

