5.2.2 Modifications to IS treatments

Mandatory and allowed (e.g., topical IS) IS therapies make up the subject's background chronic GVHD IS therapy during the study. The dose and frequency of these medications should be kept constant during the study.

Systemic glucocorticoids

Glucocorticoid dosing should not be increased or decreased during the course of the study, with the following exceptions:

- The investigator may see reason to initiate or increase the dose of systemic glucocorticoid to treat chronic GVHD flare or another condition. In this case, the investigator should consult with the sponsor prior to initiation or dose increase and the

Confidential

reason for dose increase should be documented. The subject may continue on ponesimod. The prednisone equivalent dose should never exceed 1 mg/kg/day.

- Systemic glucocorticoid dosing may be lowered to avoid or prevent short- and long-term glucocorticoid toxicity. For subjects on longer term glucocorticoid therapy, it is recommended that the dose reduction rate does not exceed 10% of dose per week. Glucocorticoid dosing may be increased following reduction, if medically indicated.
- Systemic glucocorticoid dosing is not subject to restrictions during the Extension Treatment Period.

Mandatory systemic IS other than ponesimod or systemic glucocorticoids

Systemic IS dosing (mg daily dose) should not be increased above baseline dose during the course of the study, with the following exception:

- Systemic IS blood or serum level is below the therapeutic range that was defined for the subject at the time of entry into the study. The dose should be increased to restore blood or serum levels to within the defined therapeutic range. (ISs that are not monitored with blood or serum level monitoring may never be increased above baseline dose.)

Systemic IS dosing (mg daily dose) should not be lowered during the course of the study, with the following exceptions:

- AE or intolerance due to the systemic IS. The dose should be sufficiently lowered or discontinued, per investigator judgment.
- Systemic IS blood or serum level is above the therapeutic range that was defined for the subject at the time of entry into the study. The dose should be lowered to restore blood or serum levels to within the defined therapeutic range.

Topical CNIs or glucocorticoids

- The sponsor recommends not starting or increasing dosage of topical CNI or topical glucocorticoid therapy during the course of the core study.

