- Global: Clinician Overall Severity Score decreases by 2 or more points on a 0–10 scale

The proposed general guideline for defining progression in a specific organ requires a change in score from baseline as follows:

- Skin: increase in NIH Skin Score by at least 1 point, except from 0 to 1
- Mouth: increase in Modified Oral Mucositis Score by at least 2 points

Confidential

- Liver: increase by $\geq 2 \times$ ULN for ALT, alkaline phosphatase or TBL
- Upper GI: increase in NIH Upper GI Score by at least 1 point, except from 0 to 1
- Lower GI: increase in NIH Lower GI Score by at least 1 point, except from 0 to 1
- Esophagus: increase in NIH Esophagus Score by at least 1 point, except from 0 to 1
- Lungs: decrease by at least 10% absolute value of FEV₁, as long as final FEV₁ < 70% predicted
- Eyes: increase in NIH Eye Score by at least 1 point, except from 0 to 1
- Joint/fascia: increase in NIH Joint and Fascia Score by 1 or more points or decrease in P-ROM score by 1 or more points for any site
- Global: Clinician Overall Severity Score increases by 2 or more points on a 0–10 scale

The endpoint is reached if the subject is considered a partial or complete responder at Week 24. The remaining subjects will be considered as non-responders, this includes subjects with stable disease and subjects with mixed response (defined as complete or partial response in at least one organ accompanied by progression in another organ). Patients who discontinue the study prior to the Week 24 assessment are considered non-responders.

- Need for rescue therapy for chronic GVHD
 - Rescue therapy is the addition of any new systemic or topical IS therapy or exceeding baseline dose for any non-steroid IS or exceeding glucocorticoid dose equivalent to prednisone $> 1 \text{ mg/kg/day}$

This exploratory endpoint is defined as a binary endpoint. Subjects will be considered as responders in case no rescue therapy is administered; subjects will be considered as non-responders in case subjects received a rescue therapy during the treatment phase for at least one day. Every effort will be made to collect the concomitant medications data with complete start dates in order to make sure the endpoint is derived correctly. Patients who discontinue the study prior to the Week 24 assessment are considered non-responders.

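### The rescue-therapy definition counts dosing that the protocol permits or instructs, differs between synopsis and body, and is not separated from the stopping rule in 5.1.10

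*Combined protocol and SAP*

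**What the plan says.** The endpoint in 6.3.4 is named "Need for rescue therapy for chronic GVHD". Rescue is defined in three places.

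- Section 6.3.4: "Rescue therapy is the addition of any new systemic or topical IS therapy, or exceeding baseline dose for any non-steroid IS".
- Section 11.2.3: "Rescue therapy is the addition of any new systemic or topical IS therapy or exceeding baseline dose for any non-steroid IS".
- Protocol synopsis, other exploratory efficacy endpoints: the same first limb, but the dose limb reads "exceeding baseline dose for any systemic non-steroid IS".

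Each adds a third limb for glucocorticoid above 1 mg/kg/day prednisone-equivalent. Section 11.2.3 makes the endpoint binary: rescue on at least one day of the treatment phase makes the subject a non-responder. Section 11.2.8 summarises it descriptively.

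Section 5.2.2 sets the dosing rules for the Core Treatment Period.

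- Monitored systemic IS below its target range: "The dose should be increased to restore blood or serum levels to within the defined therapeutic range".
- Topical agents: "The sponsor recommends not starting or increasing dosage of topical CNI or topical glucocorticoid therapy during the course of the core study". This is a recommendation, and 5.3.4 lists topical CNI and topical glucocorticoid as allowed.
- Systemic glucocorticoid started or increased for a GVHD flare or another condition, after consulting the sponsor: "The subject may continue on ponesimod", with a ceiling of 1 mg/kg/day.

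Section 5.1.10 then says: "Ponesimod should be prematurely discontinued before initiating rescue IS therapy or other forbidden medications during the Core Treatment Period". It refers the reader to 5.3.5, the list of forbidden therapies.

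**The concern.** An endpoint meant to show that chronic GVHD needed further treatment should not fire because a drug level drifted and the site corrected it as told. Nor should the same act be scored differently according to which section the programmer used.

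The stopping rule raises a separate issue. It uses the term rescue, and the only definition of that term is the endpoint definition. Read together, they reach treatments that other sections allow. A site that took 5.1.10 literally would stop ponesimod for permitted care. That subject could not enter the Extension, because 4.6 requires 24 completed weeks. Study participation would end at the 30-day follow-up visit (5.1.9, 8.3), which carries no GVHD activity assessment for subjects who stopped early (Table 1, note 9).

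**Working it through.** No figure in the plan rests on this point, so the check sets the texts side by side. Each act below is assumed to occur in the Core Treatment Period with glucocorticoid at or below 1 mg/kg/day.

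| Act | Status under 5.2.2 and 5.3.4 | Synopsis | 6.3.4 | 11.2.3 |
|---|---|---|---|---|
| Monitored systemic non-steroid IS raised above baseline dose to restore its level | Instructed | Rescue | Rescue | Rescue |
| Existing topical CNI increased | Discouraged, allowed | Not rescue | Rescue | Rescue |
| Topical CNI or topical glucocorticoid newly started | Discouraged, allowed | Rescue | Rescue | Rescue |
| Systemic glucocorticoid newly started | Allowed after consulting the sponsor; ponesimod may continue | Rescue | Rescue | Rescue |
| Existing topical glucocorticoid increased | Discouraged, allowed | Not rescue | Not rescue | Not rescue |

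1. **Level corrections.** The dose limb has no condition on the reason for the increase, so an instructed correction counts in 3 of 3 definitions. The indication recorded under 5.3.3 does not separate these cases, since the drug is being given for GVHD either way. The reason for a dose change is not among the items that 5.3.3 lists.

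2. **Topical CNI increases.** A CNI is a non-steroid IS, and 5.2.2 itself classes these topicals as IS. The word *systemic* is present in the synopsis and absent from the other two, so the act counts in 2 of 3 definitions.

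3. **The stopping rule.** Rows 3 and 4 meet the first limb, the addition of a new IS. Inserted into 5.1.10, both would call for stopping ponesimod first. For a systemic glucocorticoid start, 5.2.2 says the opposite in terms. For topicals there is no matching sentence, only permission to use them. Row 1 also meets the definition, although raising an existing drug is less naturally described as initiating therapy.

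4. **Which reading of 5.1.10 is likelier.** The word *other* before forbidden medications, and the pointer to 5.3.5, suggest that only forbidden agents were meant. So does the continuation permission for systemic glucocorticoids. The list of most important deviations in 11.1.3 names new systemic IS and not topical. Pulling the other way, the companion sentence for the Extension mentions forbidden medications alone, so a site could take rescue as a separate trigger in the Core. The balance favours the narrow reading, but no sentence in 5.1.10 states it.

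**The case against.** The strongest reply is that the rescue wording sits under an exploratory endpoint and nothing says it governs dosing. Section 5.1.10 ties the stop to forbidden drugs and says *should*, where the organ-specific stopping rules say *must*. The rationale for Amendment 3 records that the ban on starting or increasing topicals was lifted on purpose. This stands as the likelier intent, and it is why few stops should follow. It does not supply the missing sentence.

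A second reply is that counting every dose above baseline is simple and objective. It is, but 5.2.2 instructs some of those increases, and the endpoint claims to measure need arising from GVHD.

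A reader might go further and infer that subjects stopped under 5.1.10 leave no GVHD assessment, so that the Week 24 response rate is biased downward by a calculable amount. The documents do not support that. Under 8.2.6 an early stop still has an EOT1 visit 1 to 3 days after the last dose, with the clinician and patient GVHD forms. Whether an early EOT1 may serve as the Week 24 assessment is not settled, and Section 11 leaves derivations to the SAP. No rate of topical starts or of literal-reading stops is given, so any effect on the response rate would be invented.

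**Conclusion.** The point holds as a minor one, in three parts.

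- All three definitions score instructed level corrections as rescue.
- The synopsis contradicts 6.3.4 and 11.2.3 on topical CNI increases.
- Section 5.1.10 leaves open whether permitted topical and systemic glucocorticoid starts call for stopping ponesimod, with the narrower reading likelier.

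The effect is confined to exploratory, descriptive endpoints and to avoidable stops at any site that reads 5.1.10 literally. With 30 subjects analysed, each subject wrongly scored as rescued moves the rescue proportion by 1/30 = 3.3 percentage points, provided nothing else had made that subject a non-responder. How many that would be cannot be said from the documents.

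A reader might also infer a threat to the primary lymphocyte analysis. That would require stops before Week 12 made on the less likely reading, and nothing in the documents suggests they would be common.

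**What to change.** 1. In the synopsis, 6.3.4 and 11.2.3, exclude from rescue any increase made only to restore a therapeutic level under 5.2.2.
2. Limit the dose limb to systemic non-steroid IS in all three places. A newly started topical would still count as rescue for the endpoint.
3. Add a sentence to 5.1.10: use of topical CNI or topical glucocorticoid, and systemic glucocorticoid or level-restoring IS changes made under 5.2.2, do not by themselves require stopping ponesimod. Leave all other stopping rules unchanged, including forbidden drugs under 5.3.5, the QT rules in Appendix 3 and the ceiling of 1 mg/kg/day prednisone-equivalent. The exemption should not cover everything in 5.3.4, because that list includes QT-prolonging drugs for which Appendix 3 can require interruption.

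The cost is aligned wording in three definitions and one sentence in 5.1.10, made by protocol amendment and carried into the SAP. Item 1 also needs the reason for each systemic IS dose change to be recorded, which is a small addition to the concomitant-therapy data. Items 2 and 3 need no new data.

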6.4 Quality of life endpoints

- Change from baseline to Week 12 and Week 24 in Lee Symptom Scale for chronic GVHD [Appendix 8]
- Change from baseline to Week 12 and Week 24 in each of the patient-reported chronic GVHD symptoms (skin, eyes, mouth and genitals [Appendix 7 – Form B])
- Change from baseline to Week 12 and Week 24 in each of the patient-reported global ratings (Mild-Moderate-Severe Scale, Overall Severity Scale and 7-Point Change Scale [Appendix 7 – Form B])

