7.5.3 Patient-reported global ratings (Chronic GVHD Activity Assessment Form B)

7.5.3.1 *Patient-Reported Overall Severity Scale*

The subject will complete the Patient-Reported Overall Severity Scale at visits indicated in Table 1. Subjects are asked to score how severe their chronic GVHD symptoms are on a scale of 0–10 with 0 = chronic GVHD symptoms not at all severe and 10 = most severe chronic GVHD symptoms possible. The Patient-Reported Overall Severity Scale is part of the Chronic GVHD Activity Assessment eCRF. The Chronic GVHD Activity Assessment source document forms are in Appendix 7.

7.5.3.2 *Patient-Reported Mild-Moderate-Severe Scale*

The subject will complete the Patient-Reported Mild-Moderate-Severe Scale at visits indicated in Table 1. Subjects are asked to report if they think their overall chronic GVHD is mild, moderate or severe. The Patient-Reported Mild-Moderate-Severe Scale is part of the Chronic GVHD Activity Assessment eCRF. The Chronic GVHD Activity Assessment source document forms are in Appendix 7.

7.5.3.3 *Patient-Reported 7-Point Change Scale*

The subject will complete the Patient-Reported 7-Point Change Scale at visits indicated in Table 1. Subjects are asked to compare their current chronic GVHD symptoms to one month prior on a scale of 7: +3 = very much better; +2 = moderately better; +1 = a little better; 0 = about the same; -1 = a little worse; -2 = moderately worse; -3 = very much worse. The Patient-Reported 7-Point Change Scale is part of the Chronic GVHD Activity

Confidential

Assessment eCRF. The Chronic GVHD Activity Assessment source document forms are in Appendix 7.

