8.1.2.1 Visit 2 – Day 1 – pre-dose assessments

The investigator must check all inclusion/exclusion criteria. Pre-dose assessments include:

Confidential

Assessments performed within 48 hours prior to study drug administration (pre-dose)

- Spirometry (under the responsibility of the pulmonologist)
- DLCo (under the responsibility of the pulmonologist)
- Body weight
- Chronic GVHD Activity Assessments – physician-assessed [Appendix 7 – Form A]
- Administer Chronic GVHD Activity Assessment – Patient self-report [Appendix 7 – Form B]
- Administer LSS (subject completes the questionnaire after patient self-report but prior to any clinical assessments or interaction with health care providers, preferably while waiting for their appointment)
- Hematology and blood chemistry
- Urine or serum pregnancy test for WOCBP (must be at least 21 days and at least 7 days after Visit 1 serum pregnancy, respectively)

Assessments performed on the morning of study drug administration (pre-dose)

- PK/PD samples
- Recording of change in previous and concomitant medications since Visit 1 [see Section 5.2]
- SBP/DBP (under the responsibility of the cardiac safety assessor)
- 12-lead ECG (under the responsibility of the cardiac safety assessor)
- Recording of MOC (for WOCBP only)
- Recording of AEs/SAEs: all AEs/SAEs occurring after signing of the ICF are to be reported in the eCRF and on an SAE form, if applicable.

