11 STATISTICAL METHODS

All statistical analyses will be conducted by Actelion or by designated contract research organizations supervised by Actelion.

The Statistical Analysis Plan (SAP) will be approved prior to database lock for the final analyses. The SAP provides the full details of all analyses, data displays, and algorithms to be used for data derivations.

All data will be listed, and endpoints will be summarized by appropriate descriptive statistics (tables or figures), typically including:

- Number of non-missing observations, number of missing observations, mean, standard deviation (STD), median, Q1, Q3, minimum and maximum for continuous endpoints;
- Number of non-missing observations, number of missing observations and frequency with percentage per category (percentages based on the number of non-missing observations) for categorical endpoints;
- Number of subjects at risk, cumulative number of events, cumulative number of censored observations and Kaplan-Meier estimates of the survival function for time-to-event endpoints.

Absolute changes from baseline are defined as: post-baseline value minus baseline value, i.e., a positive sign indicates an increase as compared to baseline.

A percentage (relative) change from baseline is defined as the absolute change from baseline divided by the baseline value (if the baseline value not equal 0) multiplied by 100.

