11.2.4 Other variables

Quality of Life endpoints

The Quality of Life endpoints are defined in Section 6.4.

- Change from baseline to Week 12 and Week 24 in LSS for chronic GVHD [Appendix 8]
- Change from baseline to Week 12 and Week 24 in each of the subject-reported chronic GVHD symptoms (skin, eyes, mouth and genitals [Appendix 7 – Form B]).
- Change from baseline to Week 12 and Week 24 in each of the subject-reported global ratings (Mild-Moderate-Severe Scale, Overall Severity Scale and 7-Point Change Scale [Appendix 7 – Form B]).

PK evaluations

- C_{trough} concentrations of ponesimod at Day 1, and Weeks 4, 8, 12, 16, and 20 (all samples pre-dose), and Week 24
- Ponesimod concentration 3 hours post-dose at Day 1 and Week 12

PD evaluations

- Peripheral absolute blood lymphocyte count change from baseline (pre-dose on Day 1) to Weeks 4, 8, 12, 16, 20, 24, and FU1, and change from pre-dose Week 12 to 3 hours post-dose Week 12.
- Peripheral absolute lymphocyte count reversibility from EOT1 to FU1 all expressed in absolute change and percent change from baseline

PK/PD relationship

- The PK and selected efficacy and safety variables will be correlated with the PD (peripheral absolute lymphocyte count and magnitude of reduction of lymphocyte count). If deemed appropriate, the PK will also be correlated with selected safety variables.

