11.2.11.1.2 Patient-reported chronic GVHD symptoms scale and patient-reported global ratings scale

Absolute values and changes from baseline of both scales will be summarized descriptively in the PPS and FAS by visit.

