Appendix 7 Chronic GVHD activity assessment forms (cont'd)

AC-058C202 SITE NO: _____ SUBJECT NO: _____ VISIT #: _____ DATE: _____

CHRONIC GVHD ACTIVITY ASSESSMENT – PATIENT SELF REPORT – FORM B

Symptoms		Not Present										As Bad As You Can Imagine	
Please rate how severe the following symptoms have been in the last seven days . Please fill in the circle below from 0 (symptom has not been present) to 10 (the symptom was as bad as you can imagine it could be) for each item.		0	1	2	3	4	5	6	7	8	9	10	
Your skin itching at its WORST?													
Your skin and/or joint tightening at their WORST?													
Your mouth sensitivity at its WORST?													
Your genital discomfort at its WORST? (Women – vagina, vulva, or labia) (Men – penis)													
		What is your main complaint with regard to your eyes?											
		Please rate how severe this symptom is, from 0 (not at all severe) to 10 (most severe):											
		0	1	2	3	4	5	6	7	8	9	10	

Patient Global Ratings:

1. Overall, do you think that your chronic graft versus host disease is mild, moderate or severe? _____

- 1 = mild
- 2 = moderate
- 3 = severe

2. Please circle the number indicating how severe your chronic graft versus host disease symptoms are, where 0 is cGvHD symptoms that are not at all severe and 10 is the most severe chronic GvHD symptoms possible.

0 1 2 3 4 5 6 7 8 9 10

cGvHD symptoms
not at all severe

Most severe cGvHD
symptoms possible

3. Compared to a month ago, overall would you say that your cGvHD symptoms are: _____

- +3 = Very much better
- +2 = Moderately better
- +1 = A little better
- 0 = About the same
- 1 = A little worse
- 2 = Moderately worse
- 3 = Very much worse

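### The patient-reported 7-Point Change Scale is already a one-month change rating, so its planned change from baseline is a difference of two changes and can contradict what the patient reported

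*Combined protocol and SAP*

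**What the plan says.** Section 6.4 sets the endpoint as "Change from baseline to Week 12 and Week 24 in each of the patient-reported global ratings" and lists the ratings in brackets as "Mild-Moderate-Severe Scale, Overall Severity Scale and 7-Point Change Scale". The synopsis has the same definition, and Section 11.2.4 repeats it: "Change from baseline to Week 12 and Week 24 in each of the subject-reported global ratings".

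Section 7.5.3.3 describes the scale: "Subjects are asked to compare their current chronic GVHD symptoms to one month prior on a scale of 7". It runs from +3 (very much better) through 0 (about the same) to -3 (very much worse). The item on Form B in Appendix 7 begins "Compared to a month ago, overall would you say that your cGvHD symptoms are".

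The opening of Section 11 fixes the arithmetic: "Absolute changes from baseline are defined as: post-baseline value minus baseline value". Section 8.1.2.1 has Form B completed before the first dose at Visit 2, with no exception for this item, so a Day 1 rating will exist. For the patient-reported symptom scale and global ratings, Section 11.2.11.1.2 plans: "Absolute values and changes from baseline of both scales will be summarized descriptively in the PPS and FAS by visit".

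The clinician version is handled differently. Section 7.4.2.3 omits it at Visit 2 and states that no baseline is collected.

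**The concern.** Change from baseline suits a scale that records a state, such as the 0–10 Overall Severity Scale. The 7-Point Change Scale records a transition, so each score is already a change over the month before the visit. Its Day 1 value is the change over the month before enrolment. Subtracting one from the other does not measure how the patient has changed since Day 1.

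A table headed change from baseline invites exactly that reading. The trial has a single arm, so no control group would show the same artefact. A positive mean in that table could be taken as patient-reported improvement when patients had answered that they were the same or worse.

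**Working it through.** The documents attach no sample size, power or other figure to this endpoint, so there is no planned number to reproduce. The check applies the plan's own definition to every possible pair of scores.

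**Inputs**
- b = Day 1 rating and f = Week 12 or Week 24 rating, each an integer from -3 to +3 (Section 7.5.3.3; Appendix 7, Form B).
- d = f - b (definition of absolute change, Section 11).

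**Range.** The smallest d is -3 - (+3) = -6 and the largest is +3 - (-3) = +6. The scale has labels only from -3 to +3, so larger values have no stated meaning.

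**All pairs.** There are 7 × 7 = 49. Comparing the sign of d with the sign of f, which is what the patient reported at the visit:
- *Sign reversed*, 6 pairs. (b, f) = (-3, -2), (-3, -1) and (-2, -1) give d = +1, +2 and +1 although the patient reports worsening. (2, 1), (3, 1) and (3, 2) give d = -1, -2 and -1 although the patient reports improvement.
- *Reported change lost*, 6 pairs. Whenever f = b and neither is 0, d = 0. A patient who answers +2 at both visits shows no change.
- *Change created*, 6 pairs. Whenever f = 0 and b is not 0, d is not 0. Day 1 = -2 and Week 24 = 0 gives 0 - (-2) = +2.

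The total misread is 6 + 6 + 6 = 18 of 49.

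**Pairs with b at or below 0.** There are 4 × 7 = 28. Sign reversals number 3, all turning reported worsening into an apparent gain; 3 reported worsenings become d = 0; and 3 answers of about the same become positive. The total is 9 of 28, and all nine move in the favourable direction, because d - f = -b, which cannot be negative when b is 0 or less.

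**Effect on a mean.** The mean of d equals the mean of f minus the mean of b. The documents give no Day 1 distribution. For assumed Day 1 means of 0, -1 and -2, the table would sit 0, 1 and 2 points above the mean of the patients' own ratings.

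**With the fix.** If f is summarised without subtraction, 0 of 49 pairs are misread and the range stays -3 to +3.

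The pair counts show what the arithmetic can do. They are not expected proportions of patients.

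**The case against.** The strongest reply is that little is lost. Section 11.2.11.1.2 also summarises the absolute values by visit, and Section 11 says that all data are listed, so the patients' own ratings will be visible. Quality of life is not named among the objectives in Section 2, the analysis is descriptive with no test, about 30 subjects are planned, and other patient-reported measures are collected. Section 11 also leaves derivation algorithms to a SAP whose separate text is not in the document. All of this stands, and it is why the point is minor. It does not remove the problem, because the defined endpoint is still the difference, and the two tables could disagree in sign.

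Three stronger readings are tempting, and the documents do not support them.

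- *That stable disease will be shown as improved.* A Week 24 score of 0 means unchanged over the past month, not unchanged since Day 1. A patient who improved greatly by Week 20 and then held steady also scores 0. Moving from -2 to 0 is also a real change in course, since the worsening has stopped; it is mislabelled rather than meaningless.
- *That the bias must flatter the drug.* Inclusion criterion 5c requires progression despite at least 4 weeks of current therapy, or no improvement despite at least 8. This makes Day 1 ratings at or below zero plausible, but it is an investigator's judgement and not the patient's one-month rating. No improvement may also mean a score near 0, where subtraction does no harm.
- *That the raw score would supply change since baseline.* It covers only the month before each visit.

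**Conclusion.** The point holds as a minor one. As written, the synopsis and Sections 6.4, 11.2.4 and 11.2.11.1.2 call for subtracting one month-long change from another. The result is not change since baseline, goes beyond the labelled range of the scale, and contradicts or distorts the patient's report in 18 of 49 possible pairs, with the sign reversed in 6. This part needs no assumption beyond the definitions in the documents.

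The direction of the distortion does rest on an assumption. It favours apparent improvement only if Day 1 ratings tend to lie at or below zero. The same condition may apply in the extension, where Section 11.2.5 makes EX-1 the baseline and Section 4.6 requires progression since EOT1, again by clinical criteria rather than the patient's rating.

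The damage is confined to one descriptive quality-of-life output. No primary, safety or tested result depends on it. The protocol's decision to collect no baseline for the clinician version suggests an oversight rather than a deliberate choice.

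**What to change.** Remove the patient-reported 7-Point Change Scale from the change-from-baseline endpoints in the synopsis and in Sections 6.4, 11.2.4 and 11.2.11.1.2, and from the corresponding extension analyses. This brings it into line with the clinician version, which has no baseline.

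Keep the summary of observed scores that is already planned. Show the Week 12 and Week 24 ratings as the number and percentage in each of the seven categories, labelled as change over the past month so that they are not read as change since Day 1. Take patient-reported global change since baseline from the Overall Severity and Mild-Moderate-Severe scales, for which the subtraction is valid.

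The cost is about one sentence in each place and one fewer table. No new data or visits are needed. Section 11 has the SAP approved before database lock, so the handling can be settled there.
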